6.3 Secondary Safety Endpoints

All secondary safety endpoints will be evaluated at 36 months postoperatively.

≠ Rate of occurrence of sight-threatening adverse events including,

- Persistent (at time of study exit) BCDVA loss of 3 or more lines compared to best BCDVA achieved during the course of study
- Endophthalmitis
- Corneal decompensation
- Retinal detachment
- Severe choroidal hemorrhage or detachment
- Aqueous misdirection

$$Rate = \frac{\# \text{ of subjects who experience any sight - threatening adverse events}}{\# \text{ of subjects in ITT set}}$$

≠ Rate of ocular secondary surgical interventions (SSI)

$$Rate = \frac{\# \text{ of subjects with any ocular SSIs}}{\# \text{ of subjects in ITT set}}$$

≠ Rate of ocular SSIs associated with CyPass placement and stability

$$Rate = \frac{\# \text{ of subjects with any ocular SSIs associated with CyPass placement and stability}}{\# \text{ of subjects in ITT set}}$$

6.3.1 Secondary Safety Hypotheses

There are no statistical hypotheses for the secondary safety endpoints.

6.3.2 Analysis Methods

These endpoints will be summarized by numerator (number of eyes meeting the endpoint), denominator (number of eyes in the ITT set), and the rate of ITT eyes meeting the endpoint.

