15.4.2.2 Analysis Methods

Continuous endpoints will be summarized by number of observations (n), mean, median, standard deviation, minimum and maximum; binary endpoints will be summarized by numerator (number of eyes meeting the endpoint), denominator, and the proportion of ITT eyes meeting the endpoint. Denominators for adverse events, slit lamp findings, and other events will be the number of eyes in the ITT set. Denominators for data such as visual acuity and other subject data that is collected at protocol-required visits will reflect the number of eyes with non-missing data in the ITT set. Summary statistics will be presented at all postoperative visits for which the endpoint data are collected. Supportive analysis will be conducted using the DI analysis set for all secondary effectiveness outcomes.

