15.8 Sample Size Justification

The performance target for the primary safety endpoint is 7.0%.

An evaluation of COMPASS (TMI-09-01) data showed that through 24 months of follow-up, there were two eyes with failures to implant and eight eyes with CyPass malposition events, respectively, corresponding to the above definitions. In addition, there were four eyes with documentation of three rings visible within the first postoperative week that likely would have undergone early secondary surgical intervention due to anterior CyPass positioning under the approach documented in the Instructions for Use (IFU). Inclusion of these cases would increase the number of observed events from 10 to 14 (3.74%, 95% confidence interval: 2.1% – 6.2%). Of note, not all investigators documented the number of rings visible in the early postoperative period because this was not a study requirement (data regarding the number of rings is recorded for only 96 subjects at 1 Day and 139 subjects at 1 Week), so this number likely underestimates the number of subjects who would have been candidates for early surgical re-intervention under the new criteria described in the IFU.

Based on these considerations, the “true” event rate is assumed to be 4.0%, and the performance target is set to 7.0%. The following assumptions were used for the sample size calculation:

- ≠ Type I error = 0.05
- ≠ one-sided alternative

With a sample size of 360 subjects in the final analysis (unilateral implants only) and a performance target of 7.0%, assuming a true event rate of 4.0%, there is 80% power to reject the null hypothesis based on a one-sided alpha = 0.05-level exact test for a single proportion.

To allow for attrition over this 36-month study, a cumulative rate of up to 20% of subjects lost to follow-up is assumed, corresponding to a targeted implantation of 450 eyes in 450 subjects to achieve at least 360 eyes with 36 months of follow-up.

Annex F of ANSI standard Z80.27-2014 refers to ensuring adequate sample size so that any adverse event of a given type that occurs in the population at a rate of 1% or greater is likely to be seen in the study. With 360 subjects, there is at least 97% probability that at least one adverse event will be detected, assuming a true rate of 1.0%. There is at least 95% probability if the true rate is 0.83%.

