6.2.2 Analysis Methods

The primary safety hypothesis will be tested with an exact one-sided binomial test with type I error 0.05. This endpoint will be summarized by numerator (number of eyes meeting the endpoint), denominator (number of eyes in the ITT set), and the rate of ITT eyes meeting the endpoint. In addition, a summary of each individual complication type included in the primary safety endpoint (and a listing of these complications) will be provided.

Otherwise, no formal statistical hypothesis testing is planned for this study.

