6.4 Other Safety Outcomes

The following safety outcomes will be summarized by numerator (number of eyes experiencing the outcome), denominator (number of eyes in the ITT set), and the rate of ITT eyes experiencing the outcome.

≠ Increase from baseline IOP of 10 mmHg or greater at any time at/after 30 days postoperative

- Change in IOP from baseline at/after 30 days postoperative is defined as,

$$Change = PostOp IOP - Baseline IOP$$

- Note: for subjects having IOP change ≥ 10 mmHg at any time at/after 30 days postoperative, a subject will be counted only once for reporting this outcome across all postoperative visits..

- # BCDVA loss of 2 or more lines compared to screening (Visit 0)
 - Change in BCDVA from screening to any postoperative visit is defined as,

$$Change = PostOp BCDVA - Screening BCDVA$$

- # BCDVA loss of 2 or more lines in comparison with best recorded BCDVA at any postoperative visit.

Note: for subjects with BCDVA loss of 2 or more lines to any visit, a subject will be counted only once for reporting this worsening across all postoperative assessments.

- # Device movement, defined as a change by at least 1 in the number of CyPass rings visible (e.g., from 1 ring to 2 rings or from 3 rings to 2 rings) that does not result in clinical sequelae (e.g., secondary surgical intervention to modify device position, corneal endothelial touch by device, corneal edema leading to loss of BCDVA > 2 lines at the last postoperative visit in comparison with preoperative BCDVA, progressive endothelial cell loss, erosion of device through sclera, or device obstruction requiring secondary surgical intervention), and that is not attributable to any one or more of the following:
 - o variations in gonioscopic viewing angle or illumination
 - o changes in angle anatomy due to concomitant findings such as resolution of hyphema
 - o changes in anterior chamber depth
 - o development of focal peripheral anterior synechiae

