6.5.11 CyPass Explantation and/or Repositioning

A listing detailing subjects with CyPass explantation and/or repositioning will be provided. The listing will include the following variables: site-subject, age, sex, race, ethnicity, explantation or repositioning event, surgery date, study day, and reason. The data for this listing will be collected on the adverse events eCRF. Further details can be found in Appendix C: Data Sources.

7 Sample Size and Power Calculations

The performance target for the primary safety endpoint is 7.0%.

An evaluation of COMPASS (TMI-09-01) data showed that through 24 months of follow-up, there were two eyes with failures to implant and eight eyes with CyPass malposition events, respectively, corresponding to the above definitions. In addition, there were four eyes with documentation of three rings visible within the first postoperative week that likely would have undergone early secondary surgical intervention due to anterior CyPass positioning under the approach documented in the Instructions for Use (IFU). Inclusion of these cases would increase the number of observed events from 10 to 14 (3.74%, 95% confidence

interval: 2.1% – 6.2%). Of note, not all investigators documented the number of rings visible in the early postoperative period because this was not a study requirement (data regarding the number of rings is recorded for only 96 subjects at 1 Day and 139 subjects at 1 Week), so this number likely underestimates the number of subjects who would have been candidates for early surgical re-intervention under the new criteria described in the IFU.

Based on these considerations, the “true” event rate is assumed to be 4.0%, and the performance target is set to 7.0%. The following assumptions were used for the sample size calculation:

- ≠ Type I error = 0.05
- ≠ one-sided alternative

With a sample size of 360 subjects in the final analysis (unilateral implants only) and a performance target of 7.0%, assuming a true event rate of 4.0%, there is 80% power to reject the null hypothesis based on a one-sided alpha = 0.05-level exact test for a single proportion.

To allow for attrition over this 36-month study, a cumulative rate of up to 20% of subjects lost to follow-up is assumed, corresponding to a targeted implantation of 450 eyes in 450 subjects to achieve at least 360 eyes with 36 months of follow-up.

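### Secondary and other safety rates at 36 months divide by all ITT eyes, so events after loss to follow-up count as non-events and the rates generally understate the 36-month risk

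*SAP*

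**What the plan says.** SAP 6.3 has the secondary safety endpoints (sight-threatening adverse events, ocular SSIs, and SSIs tied to placement and stability) evaluated at 36 months. SAP 6.3.2 summarises them by numerator, "denominator (number of eyes in the ITT set), and the rate of ITT eyes meeting the endpoint". SAP 6.4 covers IOP rise of 10 mmHg or more, BCDVA loss of 2 or more lines, and device movement, and uses a "denominator (number of eyes in the ITT set), and the rate of ITT eyes experiencing the outcome". Protocol 15.5.2.2 and 15.5.3.2 give the same all-ITT denominator for both groups.

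The ITT set is every study eye with an attempted implant (SAP 2.1). Protocol 15.8 plans for attrition: "a cumulative rate of up to 20% of subjects lost to follow-up is assumed", so that 450 implanted eyes yield 360 with 36 months of follow-up. SAP section 3 imputes nothing. The tipping-point analysis in protocol 15.6 is for the primary endpoint only, and no time-to-event estimate is planned for the secondary or other safety outcomes.

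Two other rules bear on the denominator. Protocol 15.4.2.2 uses all ITT eyes for adverse events, but says that denominators for visual acuity and other data from scheduled visits "will reflect the number of eyes with non-missing data in the ITT set". SAP section 3 has a general rule that percentages use eyes with non-missing data.

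**The concern.** An eye can contribute an event only while it is followed, but here it stays in the denominator for the full 36 months. From exit onward it is in effect scored as event-free. A reader will take a rate evaluated at 36 months as the risk of the event by 36 months, and the crude proportion equals that risk only if nobody is lost or no events happen after loss.

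These are the vision-loss, sight-threatening and re-operation rates that a post-approval safety study reports. An understated rate makes the device look safer than it is.

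A second, narrower problem is that the BCDVA and IOP outcomes fall under two incompatible denominator rules. A programmer cannot follow both.

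**Working it through.** **1. The plan's own figures.** SAP section 7 states: "With a sample size of 360 subjects in the final analysis", a 7.0% target and a 4.0% true rate, "there is 80% power to reject the null hypothesis based on a one-sided alpha = 0.05-level exact test for a single proportion". The largest count that rejects with n = 360 is 17, because P(X ≤ 17 | 360, 0.07) = 0.0499. Power is P(X ≤ 17 | 360, 0.04) = 0.802. Attrition: 360 / (1 − 0.20) = 450. Both figures reproduce, so the design inputs used below are the plan's own.

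**2. Inputs.** From the documents: N = 450 ITT eyes, d = 0.20 lost, 360 completers. Assumed, because the documents give neither: the true 36-month rate p, and the timing of events and drop-out. I use p = 5% for illustration.

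**3. Formula.** With loss unrelated to risk,

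expected crude ITT rate = p × [(1 − d) + d × F],

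where F is the average share of a lost eye's 36-month event risk that falls before its exit. If a fraction e of events is perioperative (before anyone is lost) and the rest are spread evenly over 36 months, then F = e + (1 − e) × m, where m is the mean exit time of lost eyes as a fraction of 36 months. Evenly spread exits give m = 0.5. A constant drop-out rate gives m = 1/(−ln 0.80) − 0.80/0.20 = 4.481 − 4 = 0.481.

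**4. Results at d = 0.20.**

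| Assumed pattern | Factor, even exits | Factor, constant drop-out rate | A true 5% reads |
|---|---|---|---|
| No event in a lost eye is seen (F = 0) | 0.80 | 0.80 | 4.0% |
| Events evenly spread (e = 0) | 0.80 + 0.20 × 0.50 = 0.90 | 0.896 | 4.5% |
| Half of events perioperative (e = 0.5) | 0.80 + 0.20 × 0.75 = 0.95 | 0.948 | 4.7% to 4.8% |
| 80% of events perioperative (e = 0.8) | 0.80 + 0.20 × 0.90 = 0.98 | 0.979 | 4.9% |

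In counts, the first row is 5% × 360 = 18 events seen, and 18/450 = 4.0%. The relative shortfall runs from about 2% to 20%, and 20% is the limit when loss is unrelated to risk.

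**5. If loss is related to risk.** Suppose completers have a 4% risk, lost eyes have twice that, and none of the lost eyes' events are seen. The true rate is 0.80 × 4% + 0.20 × 8% = 4.8%, the crude rate is 0.80 × 4% = 3.2%, and the factor is 3.2/4.8 = 0.67.

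**6. Why completers alone are not the answer.** In the evenly spread case 450 × 4.5% = 20.25 events are seen. Dividing all of them by 360 gives 5.6%, which overstates a true 5%.

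**7. The denominator rules side by side.** For adverse-event outcomes, protocol 15.4.2.2, protocol 15.5.2.2 and SAP 6.3.2 agree on all ITT eyes. SAP Appendix C draws every secondary safety endpoint from the adverse event form, so protocol 15.4.2.2 does not conflict for that group. For BCDVA loss and IOP rise, which Appendix C draws from the visual acuity and IOP forms, protocol 15.4.2.2 and SAP section 3 point to non-missing eyes, while protocol 15.5.3.2 and SAP 6.4 point to all ITT eyes. The conflict is confined to these outcomes.

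**The case against.** The strongest defence is that a crude incidence over treated eyes is a transparent summary that the protocol itself specifies. Numerator and denominator are both shown, and SAP 4.1 adds disposition and accountability tables. Nothing is tested on these endpoints. All of that stands. It is a reason to keep the crude column, and it limits how much turns on the point. It does not make the crude proportion a 36-month risk.

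Three stronger readings are tempting, and the documents do not support them:

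- **That the 20% lost are simply counted as event-free.** The numerators are mostly ever-type counts, SAP 6.5.1 reports adverse events from consent to exit, and protocol 12.4 asks sites to try to bring exiting subjects back for the Visit 8 procedures. Only the risk after exit is missed. Early events are also plausible for some endpoints: protocol 15.8 anticipates early re-intervention for anteriorly placed devices. This argument is weaker for IOP rise, which counts only from day 30, and for persistent BCDVA loss, which is judged at exit.
- **That the error always favours the device.** Persistent BCDVA loss is defined at study exit. An early-exit measurement could score as persistent a loss that would have recovered, which pushes that component upward.
- **That the SAP departs from the protocol throughout.** Protocol 15.5.2.2 and 15.5.3.2 specify the all-ITT denominator. Protocol 15.4.2.2 sits under secondary effectiveness, and SAP section 3 is a general convention that a specific section may override. What remains is the BCDVA and IOP conflict.

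It is also fair to say that Kaplan-Meier assumes non-informative censoring. That assumption may fail, but the crude rate makes a harsher one: no risk at all after exit.

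**Conclusion.** The point holds in a limited form. Read as 36-month risks, the secondary and other safety rates will generally be too low because events after exit are scored as non-events. At the planned 20% loss, and if loss is unrelated to risk, the relative shortfall is about 2% when most events are perioperative, about 10% when events and drop-out are evenly spread, and 20% when no event in a lost eye is seen. It could be larger if eyes at higher risk are lost more often. These sizes rest on assumed timing, and the 20% is a planning figure, not an observed one. The direction is not guaranteed for exit-defined BCDVA loss.

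The denominator conflict for the BCDVA and IOP outcomes stands whatever the size of the bias. None of this affects a hypothesis test or the success criterion, since the secondary and other safety endpoints are descriptive. It is worth correcting because the correction is cheap and these rates will be quoted.

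**What to change.** - **SAP 6.3.2 and 6.4:** keep the crude ITT proportion and add a column with the Kaplan-Meier cumulative incidence at 36 months and its two-sided 95% CI, censoring at the last visit. Apply it to SSIs, to sight-threatening adverse events other than persistent BCDVA loss, and to time to first IOP rise of 10 mmHg or more and first BCDVA loss of 2 or more lines. Merely restricting the last two to eyes with an assessment would change little, because almost every eye will have some postoperative reading.
- **Persistent BCDVA loss:** report it separately, over eyes with an exit or 36-month BCDVA, and flag early-exit assessments. It has no natural event time, so it should not enter the Kaplan-Meier estimate.
- **Denominators:** reconcile protocol 15.4.2.2 and SAP section 3 (non-missing eyes) with protocol 15.5.3.2 and SAP 6.4 (all ITT eyes) for the BCDVA and IOP outcomes, so that both documents state one rule.
- **Assumption:** state that the added column assumes non-informative censoring.

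The cost is a small wording change in both the SAP and the protocol, one extra column, and rates that will look slightly less favourable. No new data are collected.

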6.4 Other Safety Outcomes

The following safety outcomes will be summarized by numerator (number of eyes experiencing the outcome), denominator (number of eyes in the ITT set), and the rate of ITT eyes experiencing the outcome.

≠ Increase from baseline IOP of 10 mmHg or greater at any time at/after 30 days postoperative

- Change in IOP from baseline at/after 30 days postoperative is defined as,

$$Change = PostOp IOP - Baseline IOP$$

- Note: for subjects having IOP change ≥ 10 mmHg at any time at/after 30 days postoperative, a subject will be counted only once for reporting this outcome across all postoperative visits..

- # BCDVA loss of 2 or more lines compared to screening (Visit 0)
 - Change in BCDVA from screening to any postoperative visit is defined as,

$$Change = PostOp BCDVA - Screening BCDVA$$

- # BCDVA loss of 2 or more lines in comparison with best recorded BCDVA at any postoperative visit.

Note: for subjects with BCDVA loss of 2 or more lines to any visit, a subject will be counted only once for reporting this worsening across all postoperative assessments.

- # Device movement, defined as a change by at least 1 in the number of CyPass rings visible (e.g., from 1 ring to 2 rings or from 3 rings to 2 rings) that does not result in clinical sequelae (e.g., secondary surgical intervention to modify device position, corneal endothelial touch by device, corneal edema leading to loss of BCDVA > 2 lines at the last postoperative visit in comparison with preoperative BCDVA, progressive endothelial cell loss, erosion of device through sclera, or device obstruction requiring secondary surgical intervention), and that is not attributable to any one or more of the following:
 - o variations in gonioscopic viewing angle or illumination
 - o changes in angle anatomy due to concomitant findings such as resolution of hyphema
 - o changes in anterior chamber depth
 - o development of focal peripheral anterior synechiae

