6 SCHEDULE OF VISITS

Procedure/Assessment	Visit 0 (-42 to -1 days) Screening	Visit 00 (Day 0) Surgery	Visit 1 (+1 day) 1 Day Follow-up	Visit 2 (+5 to 9 days) 1 Week Follow-up	Visit 3 (+21 to 35 days) 1 Month Follow-up	Visit 4 (+70 to 98 days) 3 Month Follow-up	Visit 5 (+150 to 210 days) 6 Month Follow-up	Visit 6 (+330 to 420 days) 12 Month Follow-up	Visit 7 (+690 to 780 days) 24 Month Follow-up	Visit 8 (+1050 to 1140 days) 36 Month Follow-up/Exit/Early Exit
Informed Consent	X									
Demographics	X									
Medical History	X	X	X	X	X	X	X	X	X	X
Concomitant Medications	X	X	X	X	X	X	X	X	X	X
Number of Ocular Hypotensive Medications	X ¹	X	X	X	X	X	X	X	X	X
Urine Pregnancy Test ²	X									
Inclusion/Exclusion	X									
Surgery ³ (with video)		X								
Manifest Refraction	X ¹			X	X	X	X	X	X	X
Monocular BCDVA	X ^{1,4}		X ⁵	X	X	X	X	X	X	X
Specular Microscopy ⁶	X ¹					X	X	X	X	X
Visual Field ⁷	X ¹							X	X	X
IOP (8:00 – 10:00 am)	X ¹		X	X	X	X	X	X	X	X
Slit Lamp Examination	X ¹		X	X	X	X	X	X	X	X
Gonioscopy (photographed)	X ¹	X	X	X	X	X	X	X	X	X
Fundus Examination	X ¹					X	X	X	X	X
Central Corneal Pachymetry	X ¹							X	X	X
UBM or OCT ⁸						(X)	(X)	(X)	(X)	(X)
Adverse Events	X	X	X	X	X	X	X	X	X	X
Device Deficiencies	X	X	X	X	X	X	X	X	X	X

¹ Conduct bilaterally at Visit 0 and in study eye only at postoperative visits, unless otherwise indicated.

² In women of child bearing potential only.

³ An Alcon observer may be present during surgery.

⁴ At Visit 0, if BCDVA better than 0.3 logMAR (> 85 letters read), repeat with BAT (Brightness Acuity Meter).

⁵ At Visit 1 (Day 1 Follow-up) BCDVA will be conducted as a pinhole test.

⁶ ECD may be requested in the fellow eye at follow-up on a case by case basis.

⁷ Visual field testing may be repeated between screening (Visit 0) and surgery (Visit 00), if needed.

⁸ UBM or OCT conducted if CyPass is not visible on Gonioscopy at two consecutive visits after Visit 3 (1 Month Follow-up). Images retained at site to demonstrate placement of CyPass.

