8.2.2.2 Secondary Safety Endpoints

All secondary safety endpoints will be evaluated at 36 months postoperatively.

- ≠ Rate of occurrence of sight-threatening adverse events including
 - Persistent (at time of study exit) BCDVA loss of 3 or more lines compared to best BCDVA achieved during the course of study
 - Endophthalmitis
 - Corneal decompensation
 - Retinal detachment
 - Severe choroidal hemorrhage or detachment
 - Aqueous misdirection
- ≠ The rate of ocular secondary surgical interventions (SSI)
- ≠ The rate of ocular SSIs associated with CyPass placement and stability

8.2.2.3

Other Safety Endpoints

All other safety endpoints will be evaluated at 36 months postoperatively.

- ≠ Increase from baseline IOP of 10 mmHg or greater at any time at/after 30 days postoperative
- ≠ BCDVA loss of 2 or more lines compared to screening (Visit 0)
- ≠ BCDVA loss of 2 or more lines in comparison with best recorded BCDVA at any postoperative visit
- ≠ Device movement, defined as a change by at least 1 in the number of CyPass rings visible (eg, from 1 ring to 2 rings or from 3 rings to 2 rings) that does not result in clinical sequelae (eg, secondary surgical intervention to modify device position, corneal endothelial touch by device, corneal edema leading to loss of BCDVA > 2 lines at the last postoperative visit in comparison with preoperative BCDVA, progressive endothelial cell loss, erosion of device through sclera, or device obstruction requiring secondary surgical intervention), and that is not attributable to any one or more of the following:
 - variations in gonioscopic viewing angle or illumination
 - changes in angle anatomy due to concomitant findings such as resolution of hyphema
 - changes in anterior chamber depth
 - development of focal peripheral anterior synechiae

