25. After completion of I/A, use gonioscopy to verify CyPass Micro-Stent location and confirm the absence of CyPass Micro-Stent lumen obstruction.

26. Confirm that the surgical incision is sealed by either pressure challenge testing or Seidel testing. Use a suture or ocular sealant for closure, if needed.

Apraclonidine, brimonidine, or other topical hypotensive agents may be administered at the conclusion of the procedure. Oral or intravenous ocular hypotensive agents (eg, acetazolamide) should be avoided due to the potential for postoperative hypotony. All medication use must be documented.

During the immediate preoperative and early postoperative period, the following regimen of topical anti-inflammatory ocular medication is recommended to reduce anticipated inflammation (see Table 12.1). A topical antibiotic is prescribed to reduce the risk of postoperative infection.

Table 12-1 **Medication Regimen**

Time Period	Antibiotic	Steroid	NSAID
1-3 Days Preoperatively	4 th generation fluoroquinolone (eg, moxifloxacin) QID	eg, difluprednate 0.05% QID	eg, nepafenac 0.1% TID
Surgery Day – Week 1	4 th generation fluoroquinolone (eg, moxifloxacin) QID	eg, difluprednate 0.05% QID	eg, nepafenac 0.1% TID
Week 2	N/A	eg, difluprednate 0.05% QID	eg, nepafenac 0.1% TID
Week 3	N/A	eg, difluprednate 0.05% TID	eg, nepafenac 0.1% TID
Week 4	N/A	eg, difluprednate 0.05% BID	eg, nepafenac 0.1% TID

Adjustment of the postoperative ocular medication regimen may be made as necessary for subject safety. Any change in postoperative ocular medications must be documented.

12.2.3 **1 Day Follow-up (Visit 1)**

Visit 1 must occur on the first day postoperatively. The following information will be captured at this visit. Ocular assessments will be conducted for the study eye only.

1. Document changes in concomitant medications.
2. Perform pinhole visual acuity measurement using an ETDRS chart at 4 meters.
3. Measure IOP with Goldmann tonometer between 8:00 and 10:00 am.
4. Conduct slit lamp examination.
5. Perform Gonioscopy to determine CyPass positioning (goniophotography optional at Visit 1)
6. Record any adverse events and/or device deficiencies.

NOTE: Serious adverse events (SAEs) must be entered into EDC within 24 hours of the Investigator's knowledge. Refer to Section 13 for further detail.

12.2.4 **1 Week Follow-up (Visit 2)**

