Visit 2 must occur 5-9 days postoperatively. Below is a list of study procedures to be undertaken at this visit. Ocular assessments will be conducted for the study eye only.

1. Document changes in concomitant medications.
2. Perform manifest refraction and record monocular BCDVA using an ETDRS chart at 4 meters.
3. Measure IOP with Goldmann tonometer between 8:00 and 10:00 am.
4. Conduct slit lamp examination.
5. Perform Gonioscopy (including Shaffer grading for all 4 quadrants) with goniophotography of CyPass location.

6. Record any adverse events and/or device deficiencies.

NOTE: SAEs must be entered into EDC within 24 hours of the Investigator's knowledge. Refer to Section 13 for further detail.

12.2.5 1 Month Follow-up (Visit 3)

Visit 3 must occur 21-35 days postoperatively. Below is a list of study procedures to be undertaken at this visit. Ocular assessments will be conducted for the study eye only.

1. Document changes in concomitant medications.
2. Perform manifest refraction and record monocular BCDVA using an ETDRS chart at 4 meters.
3. Measure IOP with Goldmann tonometer between 8:00 and 10:00 am.
4. Conduct slit lamp examination.
5. Perform Gonioscopy (including Shaffer grading for all 4 quadrants) with goniophotography of CyPass location.
6. Record any adverse events and/or device deficiencies.

NOTE: SAEs must be entered into EDC within 24 hours of the Investigator's knowledge. Refer to Section 13 for further detail.

12.2.6 3 Month Follow-up (Visit 4)

Visit 4 must occur 70-98 days postoperatively. Below is a list of study procedures to be undertaken at this visit. Ocular assessments will be conducted for the study eye only.

1. Document changes in concomitant medications.
2. Perform manifest refraction and record monocular BCDVA using an ETDRS chart at 4 meters.
3. Perform specular microscopy.

4. Measure IOP with Goldmann tonometer between 8:00 and 10:00 am.
5. Conduct slit lamp examination.
6. Perform Gonioscopy (including Shaffer grading for all 4 quadrants) with goniophotography of CyPass location.
7. Conduct dilated fundus examination (including C:D assessment).
8. Record any adverse events and/or device deficiencies.

NOTE: SAEs must be entered into EDC within 24 hours of the Investigator's knowledge. Refer to Section 13 for further detail.

12.2.7 6 Month Follow-up (Visit 5)

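### SAP 6.4 counts BCDVA loss at any postoperative visit with no earliest visit, so the Day 1 pinhole reading can register as vision loss

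*SAP*

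**What the plan says.** Protocol 8.2.2.3 lists two BCDVA-loss outcomes among the other safety endpoints: loss of 2 or more lines against screening, and the same loss against the best recorded BCDVA at any postoperative visit. The list opens with the statement "All other safety endpoints will be evaluated at 36 months postoperatively".

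SAP 6.4 does not carry that sentence over, although SAP 5.1.2 and 6.3 keep its equivalent for the secondary endpoints. For the first outcome SAP 6.4 says "Change in BCDVA from screening to any postoperative visit is defined as" postoperative minus screening. After the second outcome it adds that "for subjects with BCDVA loss of 2 or more lines to any visit, a subject will be counted only once". The summary for the section uses "denominator (number of eyes in the ITT set), and the rate of ITT eyes experiencing the outcome".

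On Day 1, footnote 5 to the visit schedule (Protocol Section 6, repeated in SAP Appendix A) says "At Visit 1 (Day 1 Follow-up) BCDVA will be conducted as a pinhole test". The Day 1 procedures in Protocol 12.2.3 read "Perform pinhole visual acuity measurement using an ETDRS chart at 4 meters" and include no refraction. From Visit 2 (Protocol 12.2.4) the instruction becomes "Perform manifest refraction and record monocular BCDVA using an ETDRS chart at 4 meters".

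**The concern.** A pinhole reading on the day after surgery and a refracted BCDVA are different measurements. Protocol 13.3 names corneal edema and aqueous cells and flare among the findings typically seen early after ocular surgery. If Day 1 counts, a transient reading becomes a permanent vision-loss event for that subject, because one loss at any visit is enough.

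The second outcome has a further gap. Neither document says that the best BCDVA must be recorded before the visit at which loss is assessed. A programmer who takes the best value over all postoperative visits and compares every visit with it would code recovery from a poor Day 1 reading as a loss.

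At stake is the meaning of two pre-specified safety rates in a post-approval safety study. As worded, each mixes early recovery with later loss.

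**Working it through.** **1. Does anything exclude Visit 1?** The Monocular BCDVA row in both schedules is marked at Visit 1. SAP Section 3 removes only unscheduled visits from summary tables. SAP Appendix C names the postoperative acuity form for both outcomes without restricting visits. Nothing takes Day 1 out.

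**2. How do comparable definitions treat early visits?**

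| Definition | Place | Earliest time |
|---|---|---|
| IOP rise of 10 mmHg or more | Protocol 8.2.2.3, SAP 6.4 | 30 days |
| BCDVA loss of 2 lines as an adverse event | Protocol 13.1.2, item a | 3 months, against Visit 3 |
| Mild to moderate corneal edema as an adverse event | Protocol 13.1.2, item l | 1 month |
| BCDVA loss of 2 lines as an other safety outcome | SAP 6.4 | none |

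**3. Direction.** An any-visit event is the union of the visit-level events, one of which is Visit 8. Over the same eyes, P(any visit) ≥ P(Visit 8). The excess includes every eye with a Day 1 loss that has recovered by Visit 8.

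**4. Size.** The documents give no BCDVA-loss rate, so there is no plan figure to reproduce and only an illustration is possible. Assume 450 ITT eyes (the implantation target), all with Visit 8 data; a Visit 8 loss rate p8; an independent Day 1 transient loss probability d; and no losses at other visits. Then P(any) = 1 − (1 − p8)(1 − d). The ranges for p8 and d are assumptions.

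| p8 (eyes at Visit 8) | d = 2% | d = 5% | d = 10% | d = 20% |
|---|---|---|---|---|
| 1% (4.5) | 13.4 | 26.8 | 49.0 | 93.6 |
| 2% (9.0) | 17.8 | 31.1 | 53.1 | 97.2 |
| 5% (22.5) | 31.1 | 43.9 | 65.3 | 108.0 |

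For example, with p8 = 2% and d = 5%: 1 − 0.98 × 0.95 = 0.069, and 450 × 0.069 = 31.1 eyes against 9. Across the grid the count is 1.4 to 20.8 times the Visit 8 count.

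**5. Second outcome.** Take a hypothetical eye reading 70 letters on Day 1 and 85 at every later visit. Against the best over all visits, Day 1 is 70 − 85 = −15 letters, or 3 lines at 5 letters per line, so it is coded as a loss. Against the best at an earlier visit, Day 1 has no comparator and later visits show no loss.

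**6. Denominator for a Visit 8 count.** The plan allows 20% attrition: 450 × 0.20 = 90 eyes without Visit 8. SAP Section 3 makes no imputations. Keeping all ITT eyes as denominator would count those 90 as free of loss. A 2% rate among 360 observed eyes is 7.2 eyes, and 7.2 / 450 = 1.6%.

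**7. Primary test.** The stated 80% power reproduces. With n = 360 the exact test rejects at 17 or fewer events, with alpha 0.0499 at 7% and power 0.8016 at 4%. Neither BCDVA-loss outcome enters that calculation.

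**The case against.** Several stronger conclusions are tempting, and the documents do not support them.

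- **The SAP contradicts the protocol's time point.** A reader might infer this from the missing 36-month sentence. But that sentence also heads an IOP outcome counted at any time from 30 days onward, so it can mean cumulative through 36 months. Protocol 15.5.3.2 also asks for summaries at all follow-up visits. In the second outcome, the any-visit wording is the protocol's own. The omission leaves the time point unclear and does not prove a conflict.
- **Real 36-month loss would be hidden.** It would not. SAP 6.5.10 summarizes BCDVA at every visit and lists losses of two lines or more. Persistent loss of 3 or more lines at exit is a secondary endpoint, and a 2-line loss from 3 months is a defined adverse event.
- **Most eyes would be flagged.** No figure in the documents supports this. For loss against screening, the comparator is an eye with an operable cataract, which may limit Day 1 losses after the cataract is removed. For the second outcome it depends on the reverse-order reading, and the SAP's words loss and worsening point away from that.

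Two points of wording also count against the concern. The count-once note is printed after the second outcome, so applying it to the first is an inference. Protocol 12.2.3 calls the Day 1 test pinhole acuity rather than BCDVA, so its inclusion could be disputed.

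What stands is that the schedules call it BCDVA, the note covers worsening across all postoperative assessments, and no rule settles either question. The missing floor, the mixed measurements and the unordered comparison remain even if the 36-month sentence is read as cumulative.

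**Conclusion.** The point holds as a definitional gap with a known direction. Following SAP 6.4 literally admits the unrefracted Day 1 reading to both outcomes, and for the second it allows improvement to be coded as loss. On a common denominator the any-visit rate is at least the Visit 8 rate. How far above it lies cannot be derived from the documents, and the multiples of 1.4 to 20.8 rest wholly on assumed rates and independence.

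The consequence is limited. Both outcomes are descriptive with no hypothesis, so the primary test, its alpha, power and sample size are untouched. The effect is on how two safety rates would be read.

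**What to change.** Amend SAP 6.4 before database lock:

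1. Exclude Visit 1 pinhole values from both BCDVA-loss outcomes. Visit 2 is refracted and can stay; the documents give no reason to begin at Visit 3.
2. For the second outcome, compare each visit only with the best refracted BCDVA at an earlier postoperative visit.
3. Report the Visit 8 rate, with eyes that have non-missing Visit 8 BCDVA as denominator, alongside the cumulative any-visit rate, to agree with Protocol 8.2.2.3. The non-missing denominator matches the general convention in SAP Section 3 and avoids treating missing eyes as free of loss. The two rates then have different denominators, so show both counts.

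The cost is SAP wording and programming, with no new data. The downside is that transient Day 1 losses leave these two rates. They remain in the by-visit summaries and listing of SAP 6.5.10.
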